Data analysis plan	The general biometric approach consists of evaluation of changes by descriptive statistical methods, as well as of regression analysis of parameters influencing the therapeutic success and additional subgroup analysis. By forward and backward stepwise regression, those patient and disease characteristics (baseline values of all target parameters, disease duration, previous therapies, demographic and anthropometric data, health-related quality of life etc.) will be selected which show a statistically significant partial correlation with the parameters of therapeutic success at month 3 (improvements in the number of affected joints [DAS28], HAQ, number of missed working days, and WPAI). Due to the clear temporal relation between the baseline values and the treatment effects at month 3, the selected predictors can be interpreted both as causal explanation and as prognosing factors concerning therapy-modifying influencing variables (since an reactive influence of the 3-month values on the baseline values can be ruled out). Additionally, the strength of the relationship between the predictors and the parameters of therapeutic success will be determined. The impact of the variables determined by regression analysis on the therapeutic success will be illustrated by subgroup analysis. The impact of adalimumab therapy on health-related quality of life (EQ-5D), the number of physician visits and hospitalization, the days of impairment in non-occupational activities, and the subjective symptoms (morning stiffness, pain, exhaustion/fatigue) will be descriptively evaluated and additionally analyzed by between-group comparison. Two interim analyses are planned.
Planned recruitment phase	March 2009 - March 2012
Planned study duration	March 2009 – March 2018
Product manufacturer	Abbott

3 Abkürzungen und Definitionen

AE	Adverse event
AMG	Arzneimittelgesetz
BMI	Body Mass Index
CCP	Cyclic citrullinated peptide
CRF	Case Report Form
CRO	Clinical Research Organization
CRP	C-reactive protein
DAS28	Disease Activity Score 28
DMARD	Disease Modifying Anti-Rheumatic Drug
EQ-5D	EuroQol Questionnaire 5 Dimensions
ESR	Erythrocyte sedimentation rate
FAS	Full analysis set
HAQ	Health Assessment Questionnaire
Hb	Hemoglobin
MedDRA	Medical Dictionary for Regulatory Activities
NIS	Non-interventional study
RF	Rheumatoid factor
SAE	Serious adverse event
SAP	Statistical analysis plan
SDV	Source Data Verification

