Several clinical trials have shown that adalimumab both reduces the clinical symptoms of RA and decelerates the structural destruction of the joints, thus significantly improving health-related quality of life.

Patients who had been included in a non-interventional long term study and had been treated with adalimumab under conditions of routine rheumatology practice had been suffering from RA for many years (mean disease duration 12 years) and showed a high disease activity (DAS28 = 5.8). These patients experienced a significant reduction in clinical signs and symptoms of RA after 24 months of adalimumab therapy (interim analysis July 2007). 20 % of patients were in clinical remission and over 40 % had improved in their physical functionality.

Unlike the previous RA documentation, this NIS will put added emphasis on data concerning work productivity and work ability as well as data concerning health-related quality of life. This will result in an according large-scale patient documentation form.

In order to improve quality, all filled questionnaires will be checked for completeness and missing data will be added by written query. A defined percentage of participating physicians will be audited. An independent CRO will perform double data entry, perform plausibility checks and statistically evaluate the data according to criteria determined in the protocol. The results will be published after finalization of the evaluation.

The planned documentation is a non-interventional study (NIS) according to § 4 section 23, point 3, Arzneimittelgesetz (AMG) and will be conducted in compliance with the recommendations of the Verband der forschenden Arzneimittelhersteller (Association of Research-based Pharmaceutical Companies).

6 Rationale

This NIS is designed to provide additional data on treatment effects of adalimumab in the long term treatment in patients with moderate to severe active RA under conditions of routine rheumatology care. In contrast to clinical trials, all patients treated in clinical routine will be included in the NIS, independent of comorbidities, concomitant medication, severity of their illness, or features such as age and gender.

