Course of work productivity and work ability, the course of health-related quality of life, and changes in functionality under long term treatment with adalimumab will be documented. The numbers of patients included in the NIS allow identifying and quantifying the impact of disease and patient characteristics on the therapeutic success.

7 Study Objectives

In this NIS, a long term documentation of treatment with adalimumab in RA patients over 60 months with 8 data collection points (visits) is planned. The documentation will be performed by the physician as well as by patient's self-assessment.

The primary objective is to explore the therapeutic success by interim analyses after 12 and 24 months of treatment as well as by the final analysis after 60 months of treatment. Improvements concerning the following target variables will be evaluated (with regard to the respective baseline value):

- the number of missed working days
- the self-assessed work ability (WPAI)
- the severity of clinical symptoms (number of tender and swollen joints, CRP and ESR, respectively; total score DAS28)
- Severity of functional impairment (HAQ)
- The health-related quality of life (EQ-5D)

At month 3, patient and disease characteristics will be evaluated with regard to their additional impact on changes in the number of affected joints (DAS28), in the HAQ, and in the WPAI. The impact on the number of missed working days will be evaluated at month 6.

The secondary objective is to document the therapeutic success by interim analyses at month 12 and 24 months as well as by the final analysis after 60 months. The therapeutic success will be evaluated by the following variables:

- The number of physician visits
- The number and duration of hospitalizations
- The number of days of impairment in non-occupational activities
- The duration of morning stiffness, pain, exhaustion/fatigue

- The reduction of number and dose of concomitant medication
- Patient's assessment of adalimumab therapy compared to previous therapies

Target parameters for safety evaluation of adalimumab are:

- The evaluation of safety and tolerability by the documentation and analysis of serious adverse events (SAEs) and adverse events (AEs).
- Evaluation of safety and tolerability for subgroups of patients with common frequent concomitant diseases, especially diabetes type II, cardiovascular, liver, and renal insufficiencies, and related concomitant medications.

8 Investigational Plan

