8.5 Study Conduct

8.5.1 Schedule of Observations

This NIS will be a single-arm, multi-center, prospective cohort study.

Non-interventional studies are one of several methodical instruments to collect information on drugs available on the market. Their defining characteristic is the lack of influence on the relationship between individual physicians and patients in respect to determining indication as well as choice and conduct of the treatment, while at the same time allowing for the structured and systematic collection of treatment data (see also Section 6). Adalimumab must not be prescribed for the purpose of including a patient in this NIS.

Patients will be informed about the type of therapy, alternate therapies, and risks, and they have to provide a written informed consent to the data collection on the documentation forms before the start of therapy. The presence of the written informed consent is documented on the base documentation form. Before enrollment in the NIS, the patients will be made anonymous. Abbott will only receive access to anonymous data. Abbott can only identify the patients via their patient number.

The visits are scheduled according to the recommendations of the Deutsche Gesellschaft für Rheumatologie (German Society for Rheumatology): The documentation consists of patient self-assessments as well as assessments by the physician. The following tables provide an overview of the observations to be documented by the physician ([Table 1](#)) and the patient ([Table 2](#)).

Due to long time intervals between the scheduled visits (one year after month 12), interim documentation forms will be provided for non-scheduled visits in order to document clinically significant events.

Table 1. Physician Schedule

	Month							
	0	3	6	12	24	36	48	60 ¹
Demographic data	X							
Inclusion criteria	X							
Indication HUMIRA®	X							
Medical history / change history	X	X	X	X	X	X	X	X
Radiologic findings ²	X			X	X	X	X	X
Previous RA therapies	X							
Concomitant diseases and therapies ³	X	X	X	X	X	X	X	X
Current HUMIRA® therapy ⁴	X	X	X	X	X	X	X	X
RA-related concomitant medication ⁴	X	X	X	X	X	X	X	X
Disease activity ⁵	X	X	X	X	X	X	X	X
Current joint status ⁵	X	X	X	X	X	X	X	X
Morning stiffness	X	X	X	X	X	X	X	X
Rheumatoid nodules	X							
Joint (replacement) surgery	X			X	X	X	X	X
Laboratory values: CRP, ESG, Hb-value, ⁶	X	X	X	X	X	X	X	X
Laboratory values: RF, CCP ⁶	X							

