12.4 Level of Significance

Inferential statistics will be performed at a nominal level of significance of 0.05 (two-sided). Due to the exploratory character of the analyses, the resulting p-values will not be adjusted for multiple testing.

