12.5 Biometric Concept

The general biometric approach consists of the realization of the analyses described in section 7 “Study Objectives”. The analysis principally uses descriptive statistical methods, supported by regression statistical methods and subgroup analysis.

By forward and backward stepwise regression, those patient and disease characteristics (baseline values of all target parameters, disease duration, previous therapies, demographic and anthropometric data, health-related quality of life etc.) will be selected which show a statistically significant partial correlation with the parameters of therapeutic success at month 3 (improvements in the number of affected joints [DAS28], HAQ, number of missed working days, and WPAI). Due to the clear temporal relation between the baseline values and the treatment effects at month 3, the selected predictors can be interpreted both as causal explanation and as prognosing factors concerning therapy-modifying influencing variables (since an reactive influence of the 3-month values on the baseline values can be ruled out). Additionally, the strength of the relationship between the predictors and the parameters of therapeutic success will be determined.

The impact of the features determined by regression analysis on the therapeutic success will be illustrated by subgroup analysis. Subgrouping will be done according to content-related considerations: Regarding disease activity, patients will be classified into groups with high or low DAS28 values (lower and higher 5.1 units, respectively). Regarding age, patients will be classified into groups with high or low age (lower and higher 40 years, respectively).

The impact of adalimumab therapy on health-related quality of life (EQ-5D), the number of physician visits and hospitalizations, the days of impairment in non-occupational activities, and the subjective symptoms (morning stiffness, pain, exhaustion/fatigue) will be descriptively evaluated and additionally analyzed by between-group comparison.

The tolerability analysis will be based on MedDRA coded AEs and SAEs. Incidence rates will be reported on the “Preferred Term” and “System Organ Class” levels for all patients as well as for subgroups of patients with different degrees of disease activity as well as with different previous and concomitant therapies and diseases.

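### Sections 2 and 12.5 allow stepwise-selected baseline predictors to be read as causal and therapy-modifying, which this single-arm study cannot support; the same text misplaces missed working days at Month 3

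*Combined protocol and SAP*

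**What the plan says.** Section 12.5 of the combined protocol and SAP, and the data analysis entry of the synopsis (Section 2), describe a forward and backward stepwise regression. Baseline characteristics are kept if they have a significant partial correlation with improvement at Month 3. The candidate list is open-ended and includes "baseline values of all target parameters". Both places then state that "the selected predictors can be interpreted both as causal explanation and as prognosing factors concerning therapy-modifying influencing variables". The only reason given is temporal order: Month 3 values cannot have influenced baseline values.

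Four other statements bear on this:

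- Section 8.5.1: "This NIS will be a single-arm, multi-center, prospective cohort study".
- Section 7: "Improvements concerning the following target variables will be evaluated (with regard to the respective baseline value"), so the outcomes are changes from baseline.
- Section 12.4: testing is at a nominal two-sided 0.05 and, because the analyses are exploratory, "the resulting p-values will not be adjusted for multiple testing".
- Section 12.5: the selected features are illustrated by subgroups, in which "patients will be classified into groups with high or low DAS28 values (lower and higher 5.1 units, respectively").

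On timing, Sections 2 and 12.5 list missed working days among the Month 3 outcomes. Section 7 limits Month 3 to affected joints (DAS28), HAQ and WPAI, and puts missed working days at Month 6.

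**The concern.** The sentence is the plan's interpretation rule for its predictor analysis, and it makes two claims that need separate treatment.

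**Causal explanation.** Temporal order is necessary for causation but not sufficient. Baseline characteristics were not assigned. Previous biologic therapy, which the synopsis singles out for evaluation, goes to patients who differ in many other ways. Confounding is therefore untouched. Selection by unadjusted significance adds false positives, and a natural course that differs across levels of a predictor would also produce an association.

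**Therapy-modifying.** Effect modification means that the treatment effect differs by level of the predictor. With no untreated or comparator group, no predictor-by-treatment interaction can be estimated, so a prognostic factor and a modifier look the same.

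A further difficulty is mechanical. An outcome's own baseline is a candidate predictor of its change, and the two are correlated by construction.

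What is at stake is the conclusion in the final report. Under the rule as written, an association produced by any of these routes could be presented as a cause of response or a modifier of adalimumab's effect.

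**Working it through.** The plan gives no figure to reproduce here. The defect lies in the reasoning, and the numbers below only show how large the non-causal associations could be.

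**Inputs from the documents.** Two-sided alpha 0.05, unadjusted (Section 12.4). Baseline/follow-up correlation r = 0.5, given for missed working days only (Section 12.1). Mean baseline DAS28 of 5.8 in an earlier documentation (Section 5: patients "showed a high disease activity (DAS28 = 5.8")). Subgroup cut at 5.1 (Section 12.5). Employed share 30% of 2500 = 750 (Section 12.1).

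**Assumptions.** r from 0.3 to 0.7; ratio k = SD(follow-up)/SD(baseline) from 0.8 to 1.25; DAS28 SD from 1.0 to 1.5; 10, 20 or 30 candidates. The documents give none of these for Month 3 DAS28, HAQ or WPAI. The treatment effect is taken as identical in every patient.

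**(a) Own baseline X against change Y − X.**

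corr = (r·k − 1) / √(1 + k² − 2·r·k)

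| r | k | corr | R² |
|---|---|---|---|
| 0.3 | 1 | −0.59 | 35% |
| 0.5 | 1 | −0.50 | 25% |
| 0.7 | 1 | −0.39 | 15% |
| 0.5 | 0.8 | −0.65 | 43% |
| 0.5 | 1.25 | −0.33 | 11% |
| 0.3 | 0.8 | −0.71 | 50% (maximum) |
| 0.7 | 1.25 | −0.14 | 2% (minimum) |

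In simulated samples of 750 with r = 0.5 and k = 1, this correlation was significant every time.

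**(b) Subgroups split at DAS28 5.1.** Under bivariate normality the difference in mean improvement, high minus low, is

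(1 − r·k) · SD · φ(z) / [Φ(z)(1 − Φ(z))], with z = (5.1 − 5.8)/SD.

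- SD 1.2, r 0.5, k 1: z = −0.583 and 0.50 × 2.00 = 1.0 point.
- Minimum (SD 1.0, r 0.7, k 1.25): 0.125 × 1.70 = 0.21.
- Maximum (SD 1.5, r 0.3, k 0.8): 0.76 × 2.46 = 1.87.

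No effect modification is present in any of these cases.

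**(c) Chance selection.** With K independent null candidates, 0.05·K are expected to be significant, and at least one is with probability 1 − 0.95^K.

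| K | Expected | At least one |
|---|---|---|
| 10 | 0.5 | 40% |
| 20 | 1.0 | 64% |
| 30 | 1.5 | 79% |

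Simulated forward/backward selection on pure noise (n = 750, 1000 runs each) gave 39%, 67% and 79%.

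**(d) Confounding.** Suppose an unmeasured cause correlates 0.4 (assumed) with both a predictor and the outcome, and the predictor itself has no effect. The induced correlation is 0.4 × 0.4 = 0.16. It was significant in 99% of simulated samples of 750. This predictor also precedes the outcome, so the plan's temporal argument would accept it.

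**Timing of missed working days.**

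| Place | Time point |
|---|---|
| Section 2, data analysis | Month 3 |
| Section 12.5 | Month 3 |
| Section 7 | Month 6 |
| Table 2 | Collected at Month 0 and from Month 6; six-month recall; no Month 3 entry |
| Section 8.5.2 | Collected at baseline and from Month 6 |

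The WPAI is collected at Month 3 and asks about hours missed, but it covers seven days and is listed separately, so it does not resolve the conflict.

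**The case against.** The strongest reply is that nothing planned would be computed differently. The sentence is permissive, the analyses are labelled exploratory and mainly descriptive, and a detailed SAP must be approved before the first interim analysis. No primary estimate or sample size depends on it. That is a fair argument about weight. It does not remove the defect: Section 12.4 uses the exploratory label to explain the lack of multiplicity adjustment, and no passage withdraws the causal reading or says the SAP will.

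Several objections to the illustrations are valid:

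- Most inputs are assumed and the ranges are wide.
- Candidates such as DAS28, HAQ, EQ-5D and WPAI are probably correlated, whereas (c) assumes independence. The stepwise entry and removal thresholds are not stated, and 0.05 is inferred from Section 12.4.
- The outcome may be the joint count rather than total DAS28. The 1.0-point figure would then not describe it, although the own-baseline mechanism in (a) applies to any change score.
- The plan says the subgroups illustrate the selected features. It does not itself call the 5.1 contrast evidence of effect modification. The risk comes from combining that contrast with the interpretation sentence.
- A natural course common to all patients creates no predictor association; only one that varies with the predictor does.

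The Month 3/Month 6 conflict is also minor. Section 12.5 says it carries out the Section 7 analyses, and the item is not collected at Month 3, so only one reading is workable. It remains a contradiction in the text.

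**Conclusion.** The concern holds. Temporal order excludes reverse causation and nothing more. The causal reading fails because of confounding and significance-based selection; the therapy-modifying reading fails because there is no comparator. These conclusions follow from the design and the wording, and need no assumed number.

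The size is illustrative only. The calculations show that associations large enough to be selected, or to look clinically notable, can arise with a uniform treatment effect. The central values rest on r = 0.5, equal SDs, a DAS28 SD of 1.2 and 20 independent candidates. The wide ranges reflect what the documents do not give.

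The correction should be made, but it concerns what may be concluded. Reporting the selected variables as exploratory prognostic associations remains legitimate. The timing of missed working days is a separate, smaller inconsistency.

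**What to change.** In Sections 2 and 12.5, remove the causal and therapy-modifying interpretation and the temporal-order argument for it, and say that selected predictors are reported as exploratory prognostic associations. Add that neither the coefficient of an outcome's own baseline nor the contrast between the DAS28 5.1 subgroups is evidence of effect modification. Carry the same wording into the SAP.

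In the same two sections, take missed working days out of the Month 3 list and assign it to Month 6, matching Section 7, Table 2 and Section 8.5.2.

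Forcing each outcome's own baseline into its model is optional. It cures neither confounding nor stepwise selection, and hardly changes the other coefficients if baseline would be selected anyway.

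The cost is wording in two sections plus matching SAP text, with no new data. The study gives up a causal claim that it could not support.

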8.1 Selection of Study Population

This study population will consist of adult patients (≥ 18 years) with moderate to severe active rheumatoid arthritis (RA) who have failed other anti-rheumatic drugs including Methotrexat (MTX) and patients with a severe, active and progressive rheumatoid arthritis (with or without prior MTX).

Patients who have been previously treated with other biologics (including TNF inhibitors) can be included in the NIS.

The inclusion and exclusion criteria adhere to the approved label as stated in the German Summary of Product Characteristics (SPC) “Fachinformation” for HUMIRA®. No additional inclusion and exclusion criteria are applicable since this project is non-interventional.

Patients to be included will be informed about the NIS and the use of their anonymous data. Patients willing to participate must provide their written informed consent to the investigator before entry into the NIS. The signed informed consent form will be added to the patient's file.

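### In this single-arm cohort, neither a variable's own-baseline slope nor the DAS28-change contrast at 5.1 can be told apart from regression to the mean, so neither supports a causal or therapy-modifying reading

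*Combined protocol and SAP*

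**What the plan says.** All references are to the combined protocol and SAP (Documentation Plan AGIL).

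- **Design.** Section 8.5.1: "This NIS will be a single-arm, multi-center, prospective cohort study". There is no comparator.
- **Outcomes modelled.** Section 12.5 models change at month 3: "improvements in the number of affected joints [DAS28], HAQ, number of missed working days, and WPAI".
- **Candidate predictors.** The same section offers "baseline values of all target parameters, disease duration, previous therapies, demographic and anthropometric data" and more. Each outcome's own baseline is therefore a candidate predictor of its own improvement.
- **Planned reading.** On the ground that month-3 values cannot act back on baseline values, Section 12.5 states that "the selected predictors can be interpreted both as causal explanation and as prognosing factors concerning therapy-modifying influencing variables".
- **Display.** Regression-selected features are then illustrated by subgroups: "patients will be classified into groups with high or low DAS28 values (lower and higher 5.1 units, respectively". The word baseline is not printed beside 5.1. It is inferred, because the subgroups illustrate baseline features.
- **Context.** In the earlier adalimumab cohort described in Section 5, patients "showed a high disease activity (DAS28 = 5.8". Section 6 presents quantifying the impact of patient and disease characteristics on therapeutic success as something the cohort size makes possible.
- **Safeguards.** Neither document mentions regression to the mean or a baseline-adjusted model of the follow-up value. Section 12.4 calls the analyses exploratory, but only to justify unadjusted p-values.

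**The concern.** Improvement contains the baseline value. Measurement error and short-term fluctuation at baseline therefore enter both sides of the regression, and patients who measure high at baseline tend to fall further on re-measurement whatever the drug does. The plan's temporal argument rules out reverse causation. It does not remove this coupling.

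Followed as written, the stepwise procedure will very probably select own baseline, the plan permits that to be reported as a therapy-modifying factor, and the 5.1 subgroups will seem to confirm it. The natural message would be that adalimumab works better in more active disease. The analysis cannot support that message, and patients with lower baseline activity may in fact reach the better state.

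**Working it through.** **The plan's own figures.** The plan gives no number for this analysis. The closest inputs are in Section 12.1: missed working days with mean 26, SD 55, and baseline/follow-up correlation r = 0.5. The sample size stated there does not reproduce with the paired formula: SD of change = 55 × √(2 × (1 − 0.5)) = 55, and n = ((1.960 + 0.842) × 55 / 5)² ≈ 950, against 850 stated. That is a separate matter and does not affect what follows.

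**Step 1: coupling of own baseline with improvement.** Let B be baseline, F follow-up, D = B − F, with equal variances σ² and the same effect in every patient.

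- Cov(D, B) = σ²(1 − r) and Var(D) = 2σ²(1 − r).
- Slope of D on B = 1 − r; corr(D, B) = √((1 − r)/2).
- With r = 0.5: slope 0.5, correlation √0.25 = 0.50, 25% of variance.
- At n = 850: t = 0.50 × √(848 / 0.75) = 16.8, so selection is practically certain.
- A patient 1 SD above the mean (26 + 55 = 81 days) is expected to improve by 0.5 × 55 = 27.5 days with no drug effect. The planned detectable difference is 5 days.
- As a check, Cov(D, (B + F)/2) = (Var B − Var F)/2 = 0. Regressing D on the average of the two values (Oldham's method) removes the association; simulation gave 0.00, against 0.50 with baseline as predictor.

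**Step 2: the DAS28 split.** Mean 5.8 is from Section 5 (the earlier cohort). The SD (1.0 to 1.4), the slope of follow-up on baseline (0.8 to 0.3) and normality are assumptions; the documents give none of them for DAS28. With a = (5.1 − 5.8)/SD, the baseline difference between groups is SD × φ(a) / [Φ(a)(1 − Φ(a))], and the contrast in change under an equal effect is (1 − slope) times that.

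| SD | Baseline difference | Slope 0.8 | Slope 0.5 | Slope 0.3 |
|---|---|---|---|---|
| 1.0 | 0.3123 / (0.2420 × 0.7580) = 1.70 | 0.34 | 0.85 | 1.19 |
| 1.2 | 2.00 | 0.40 | 1.00 | 1.40 |
| 1.4 | 2.31 | 0.46 | 1.16 | 1.62 |

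Even the smallest contrast would be clearly significant. With SD 1.0, r = 0.8 and 800 patients (the interim group size in Section 12.6), 76% lie above 5.1 and z = 0.34 / (√0.4 × √(1/606 + 1/194)) ≈ 6.5.

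**Step 3: change and level reached point in opposite directions.** Take SD 1.2, slope 0.5 and a common effect E. Baseline means are 6.36 and 4.36. Improvement is E + 0.5 × (6.36 − 5.8) = E + 0.28 above 5.1, and E + 0.5 × (4.36 − 5.8) = E − 0.72 below. Levels reached are 6.08 − E and 5.08 − E. The high group improves 1.00 more and still ends 1.00 worse.

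**Step 4: why own baseline should stay as a covariate.** If F = α + βB + γx, then B − F = −α + (1 − β)B − γx. Any other predictor x has the same coefficient in both models apart from sign. In a simulation (n = 2500) with x related to baseline but with no effect given baseline, the coefficient of x on improvement was 0.16 (p about 10⁻¹²) without baseline in the model and −0.002 (p = 0.93) with it.

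**Step 5: missed days.** A mean of 26 with SD 55 cannot be normal, since 32% would be negative. Under assumed skewed shapes the share with fewer than 5 days, who cannot improve by 5, is 27% (lognormal), 54% (gamma) or 66% (zero-inflated exponential).

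**The case against.** **The pattern may be real.** A drug that truly halved every DAS28 would also give a follow-up slope of 0.5, and the same 0.85 to 1.16 contrast as genuine absolute benefit. This stands. A reader might infer that the high-baseline finding would be an artefact, but the documents do not show that. They support only that the slope and the contrast cannot separate the two explanations.

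**Own baseline is a legitimate covariate and prognostic variable.** This also stands (Step 4). The fault lies in reading its coefficient as causal or therapy-modifying, not in having it in the model. For missed days, stepwise omission is unlikely (t = 16.8). Forcing it in secures the point for every outcome.

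**The reach is limited.** Section 12.5 is principally descriptive, and the subgroups only illustrate. The coupling is direct only for DAS28 change split by DAS28. For HAQ, WPAI or missed days split by DAS28, any effect depends on cross-correlations that are not given. The whole-cohort mean changes named as primary in Section 7 are not altered by these choices.

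**Entry at a disease peak is not shown.** Section 8.1 describes patients with "moderate to severe active rheumatoid arthritis (RA) who have failed other anti-rheumatic drugs", which is compatible with persistent activity. The 5.1 contrast arises without any entry selection, so the point does not need it.

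**Detail is deferred and the work is exploratory.** Section 12 leaves procedures to a later SAP, which makes the change easy. It does not cancel the interpretive sentence already written, and the exploratory label covers only multiplicity.

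**Conclusion.** The concern holds in a limited form. Section 12.5 permits a causal and therapy-modifying reading that this design cannot support for an outcome's own baseline or for DAS28 change above and below 5.1.

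The size is a correlation of 0.50 between own baseline and missed-day improvement under an identical effect in everyone. That rests on the plan's r = 0.5 and equal variances; r is stated for missed days only. For DAS28 the contrast in change is about 0.3 to 1.6 units with no difference in effect. That range rests on the earlier cohort's mean and on assumed SD, slope and normality, and is driven mainly by the slope.

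Three stronger readings are not supported:

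- A DAS28 floor effect is plausible but cannot be sized from the documents.
- Setting the contrast against the amendment's 1.8-point criterion is inapt, because that is a within-patient response threshold and not a difference between group means.
- The overall treatment-period changes are not invalidated by this point.

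**What to change.** In Section 12.5, or in the SAP before the first interim analysis:

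1. Force the baseline value of the same variable into every model as an adjustment covariate, outside the stepwise choice, preferably with the follow-up value as outcome.
2. Do not report that coefficient as a predictor of therapeutic success. Delete or restrict the sentence that selected predictors can be interpreted as causal or therapy-modifying.
3. Define the 5.1 split explicitly on baseline DAS28. Assign a value of exactly 5.1, and correct the order of the labels, which read literally attaches lower values to the high group. Show the DAS28 level reached beside the change, and state that a difference in change is expected from regression to the mean.
4. Report the share of employed patients with zero missed days at baseline beside missed-day improvement. At the same time, reconcile the time point: Section 12.5 models missed days at month 3, Section 7 at month 6, and Table 2 does not collect them at month 3.

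The cost is SAP wording, one extra display column and a more cautious interpretation. The data collected and the number of models do not change.
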